11.1.6.2. Analyses of Secondary Efficacy Endpoints

Median DOR, PFS and OS will be estimated using the Kaplan-Meier method.

- DOR is defined as the time from the date on which objective response (CR or PR) is first determined until the first date on which radiographic disease progression is determined, and will only be calculated for subjects with a confirmed objective response. Subjects achieving a confirmed objective response who do not have radiographic disease progression will be censored at the date of the last available post-baseline evaluable tumor assessment. DOR will be analyzed using Kaplan-Meier methods.
- PFS, defined as the time from first dose date until the first occurrence of either radiographic or clinical disease progression as determined by the Investigator or death from any cause before discontinuation from treatment. PFS for surviving subjects without disease progression will be censored at the date of the last available post-baseline evaluable tumor assessment. Surviving subjects without any post-baseline disease assessment will be censored on Day 1.
- OS is defined as the time from first dose date until death from any cause. OS data from surviving subjects will be censored at time of the last contact.
- DCR is defined as the proportion of subjects who achieve CR, PR, or stable disease, and will be analyzed using the same method as ORR.

Descriptive summaries will be provided for estimation of ORR, DOR, DCR and PFS based on RECIST v1.1 and irRC.

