#### Progression-free Survival per RECIST v1.1

Progression-free survival (PFS), defined as the time from the first dose date until the first occurrence of either radiographic or clinical disease progression or death from any cause during the treatment period. Subjects without PFS event by the analysis cut-off date will have their PFS censored at the last evaluable post-baseline tumor assessment day or on Day 1 if they have no post-baseline tumor assessments. PFS (in months) will be calculated as:

```
(Event date or censoring date – First dose date + 1) / 30.4375
```

Because the dosing interval between cycles without a dose is 7 days (from Day 15 to Day 21 of each cycle), the treatment period will include 7 days after the last dose date. Thus, subjects who are not radiologically or clinically progressed, but died within 7 days of the last dose will be considered as having PFS events. Deaths after 7 days of last dose without radiological or documented clinical progression will not be considered as PFS events in the primary PFS analysis. Table 3 below describes the scheme of events and censoring for PFS.

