#### Progression-free Survival per irRC

PFS per irRC will be defined analogous to PFS per RECIST v1.1 by replacing RECIST v1.1 progression by irRC progression (irPD). In the schema shown in Table 3, replace 'radiological' disease progression per RECISIT v1.1' by irPD and 'First date of radiological disease progression' by 'First date of irPD'.

Outcome	Situation	Date of Progression or Censoring
PFS Event	Radiological disease progression per RECIST v1.1 at scheduled or unscheduled visits or at End of Treatment visit	The earliest date of radiological disease progression, documented clinical progression, or death
	Documented clinical progression	
	No radiological or documented clinical disease progression, do not die within 7 days of the last dose, and have adequate tumor assessment at both Baseline and post-Baseline	Date of last adequate tumor assessment
Censoring for PFS (If no PFS	Discontinuation of treatment due to reasons other than radiological disease progression, or documented clinical progression	
Event)	Death after 7 days of the last dose	
	No documented clinical disease progression, do not die within 7 days of the last dose, and had no adequate tumor assessment at either Baseline or post-baseline	First dose date

Table 3:Scheme of Events and Censoring for PFS per RECIST v1.1

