#### 4.9.2 Extent of Exposure

Extent of exposure will be summarized for treatment duration, number of cycles initiated, number of doses administered, dose reductions, dose delay, cumulative dose, weight adjusted

cumulative dose, average dose intensity, and relative dose intensity by cancer type and in total separately for the Dose Escalation portion and the Dose Expansion portion.

An overall summary of drug exposure will be presented for the number of cycles initiated with any study medication and duration of treatment for all study medications. Duration of treatment is defined as the time from first dose date of any study medication to the last dose date of any study medication. Overall drug exposure will be summarized using descriptive statistics. The frequency count and percentages will also be presented for subjects who had number of treatment cycles initiated  $>0, \geq 2, \geq 4$ , etc.

For each study medication (PEGPH20 and pembrolizumab), exposure will be summarized using descriptive statistics by cancer type and in total for the following parameters across all cycles.

- Number of cycles initiated
- Duration of treatment
- Number of doses administered
- Frequency and percentage of subjects with at least one dose omitted

For subjects with at least one dose omitted:

- Total number of expected doses up to the last dose received, including doses omitted
- Frequency and percentage of doses omitted
- Frequency and percentage of dose omission by reason, including PEGPH20 toxicity, chemotherapy toxicity, other adverse event, scheduling conflict, discontinued PEGPH20 and other
- Frequency and percentage of subjects with at least one dose PEGPH20 reduction

For subjects with at least one PEGPH20 dose reduction:

- Total number of doses administered
- Frequency and percentage of doses with dose reduction
- Frequency and percentage of subjects with at least one dose delay. A treatment cycle is considered delayed if the first dose date of the following cycle is greater than 28 days after the first dose date of the cycle of interest.

For subjects with at least one dose cycle delay:

- Total number of cycles initiated
- Frequency and percentage of cycles with dose delay
- Frequency and percentage of subjects with at least one dose interruption

For subjects with at least one dose interruption:

- Total number of doses administrated
- Frequency and percentage of doses with dose interruption

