- Frequency and percentage of dose interruption by reason, including adverse event and other
- Frequency and percentage of interrupted doses restarted
- Actual dose intensity (ADI) per cycle is defined as the cumulative dose divided by number of adjusted treatment cycles.
  - The weight-adjusted cumulative dose administered for PEGPH20 (in both Dose Escalation and Dose Expansion portions) and pembrolizumab (in the Dose Escalation portion only) is the sum of the respective doses administered at a given visit, divided by the subject's weight measurement (kg) at Screening. Cumulative dose for pembrolizumab (in the Dose Expansion portion only) is defined as the sum of administered doses.
  - If the last dosed cycle is Cycle 1, then number of adjusted treatment cycles is considered to be 1. If the last dosed cycle is Cycle 2 or beyond, then the number of adjusted treatment cycles will be calculated as [(End date of last cycle First dose date + 1) / 21], where the end date of last cycle is calculated as [First dose date of last cycle + (Number of doses received or omitted in the last cycle up to the last dose received) \* 20 / 3] for PEGPH20 and (Dose date + 20) for pembrolizumab. For PEGPH20, if the day of the visit of first dose date of last cycle is not 1, then an adjustment should be made by subtracting 7 or 14 depending on whether the day is 8 or 15 respectively.
- The planned dose intensity (PDI) for PEGPH20 is calculated as follows:
  - For the Dose Escalation portion, if the number of adjusted treatment cycles is 1, then the planned dose intensity per cycle (ug/kg) for each individual dosing cohort will be calculated as [(Dose level in ug/kg) \* Number of doses received or omitted up to the last dose received in Cycle 1]. Else, the planned dose intensity per cycle (ug/kg) for each individual dosing cohort will be calculated as [(Dose level in ug/kg) \* 3].
  - For the Dose Expansion portion, if the number of adjusted treatment cycles is 1, the planned dose intensity per cycle (ug/kg) will be calculated as [(RP2D dose in ug/kg) \* Number of doses received or omitted up to the last dose received in Cycle 1]. Else, the planned dose intensity per cycle (ug/kg) will be calculated as [(RP2D dose in ug/kg) \* 3].
- The PDI for pembrolizumab is calculated as follows:
  - For the Dose Escalation portion, the planned dose intensity per cycle is 2 mg/kg.
  - For the Dose Expansion portion, the planned dose intensity per cycle is 200 mg.

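### The SAP's 7-day cut-off censors on-treatment deaths that the Protocol counts as PFS events, does not name the drug behind the last dose, and is not listed as a change

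*SAP*

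**What the plan says.** **Protocol 11.1.6.2** counts as PFS events radiographic or clinical progression and "death from any cause before discontinuation from treatment". It sets no day limit. Its censoring rule covers only subjects who are alive: "PFS for surviving subjects without disease progression will be censored at the date of the last available" evaluable post-baseline scan.

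**SAP 4.7.1 (PFS per RECIST v1.1)** defines the treatment period as the last dose date plus 7 days and gives the reason: "Because the dosing interval between cycles without a dose is 7 days (from Day 15 to Day 21 of each cycle". It then states: "Deaths after 7 days of last dose without radiological or documented clinical progression will not be considered as PFS events". Table 3 puts "Death after 7 days of the last dose" under censoring. Such a subject is censored at the last adequate scan, or at first dose if there is none. PFS per irRC follows the same scheme.

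**SAP 4.9.2 (Extent of Exposure)** uses longer intervals. On delays it says: "A treatment cycle is considered delayed if the first dose date of the following cycle is greater than 28 days after" the first dose of the cycle in question. For dose intensity, the end of the last cycle depends on the number of doses "for PEGPH20 and (Dose date + 20) for pembrolizumab". Treatment duration there runs "to the last dose date of any study medication", whereas the PFS text names no drug.

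**SAP Section 5** lists two changes from the Protocol: the Tumor Response Evaluable Population and the source of laboratory data. Neither concerns PFS.

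**The concern.** Seven days is the gap between doses only when every Day 15 PEGPH20 dose is given and the next cycle starts on time. In a longer gap, a subject can die from day 8 onward while still on study treatment. The Protocol makes that death an event. The SAP moves the subject back to the last scan and censors there.

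The mismatch also runs the other way. A death within 7 days of the last dose but after formal discontinuation is an event under the SAP only. The net direction against the Protocol is therefore unknown. Censoring a death in a dosing gap is likely to be informative, however, because the subject may have missed doses through being unwell. That tends to flatter the Kaplan-Meier curve.

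The planned PFS and OS listings would let a reader trace these deaths by hand, but no table counts them.

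**Working it through.** **1. The SAP's 7 days.** Day 15 to Day 21 inclusive is 21 - 15 + 1 = 7 days, and Day 15 to the next Day 1 (Day 22) is also 7. The figure reproduces for a schedule kept exactly.

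**2. Days left uncovered in longer gaps.** For g days between doses, a death on days 0 to 7 after the dose is an event and a death on days 8 to g - 1 is censored. The uncovered share is (g - 8)/g for g of 8 or more.

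| Gap | Source | g | Uncovered |
|---|---|---|---|
| Day 15 to Day 22 | nominal schedule | 7 | 0 |
| Day 13 to Day 24 | ±2-day visit window, Protocol Table 5 | 11 | 3/11 = 27% |
| Day 15 to Day 29 (28-day cycle), or Day 8 to Day 22 with Day 15 omitted | SAP 4.9.2; Protocol Table 6 | 14 | 6/14 = 43% |
| Pembrolizumab alone, or Day 8 and Day 15 PEGPH20 both held | Protocol 7.3.1, 8.3.2.1, Table 6 | 21 | 13/21 = 62% |
| Day 15 to Day 42 (next cycle 20 days late) | delay under 21 days, Protocol 7.3.1 | 27 | 19/27 = 70% |

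Under the Protocol rule the uncovered share is zero in every row. These are shares of days. They are shares of deaths only if the risk of death is constant across the gap. If the last dose meant PEGPH20 only, a subject continuing on pembrolizumab alone would be uncovered from day 8 for as long as treatment lasted.

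**3. Effect per death on 6-month PFS.** Cohort sizes are the Dose Expansion enrolment in SAP 4.7.2: 17 NSCLC and 25 gastric. Progression is exponential. For NSCLC the median is 3.7 months (Protocol 4.6.1). For gastric it is set from 24% PFS at 6 months (Protocol 4.6.2): 6 × ln 2 / ln(1/0.24) = 2.91 months. Progression is detected at the next scan (weeks 6, 12, 24, 36 and so on). One or two subjects die on treatment without progression, at 8 days plus an exponential time with median 2 months (assumed). Each of 20,000 simulated trials is analysed both ways: death as an event (Protocol), and censored at the last scan or Day 1 (SAP). The mean difference, SAP minus Protocol, is:

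| | one death | two deaths |
|---|---|---|
| NSCLC, n=17 | +2.4 points (5th to 95th percentile 0 to 4.7) | +5.0 |
| Gastric, n=25 | +1.4 points (0 to 2.9) | +2.8 |

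If these subjects may instead progress before their drawn death time, one death gives about +1.8 and +0.9. With no such deaths the effect is zero.

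**4. Against sampling error.** The approximate 80% CI half-width is 1.2816 × √(p(1 - p)/n).
- NSCLC: p = 0.5^(6/3.7) = 0.325, giving 1.2816 × √(0.325 × 0.675/17) = 14.6 points.
- Gastric: 1.2816 × √(0.24 × 0.76/25) = 10.9 points.

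**5. A separate matter common to both documents.** Neither counts a progression-free death after discontinuation as a PFS event (apart from the SAP's 7 days), and both end DOR only at radiographic progression. As an illustration, suppose 10% or 20% of first events are unprogressed deaths, the median time to stopping is 2 months, and half of subjects have an End of Treatment scan. The SAP rule minus an analysis counting all deaths, at 6 months, is then:

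| Death after last dose | NSCLC (10% / 20%) | Gastric (10% / 20%) |
|---|---|---|
| 14 days | +4.1 / +8.5 | +3.4 / +7.2 |
| 90 days | +2.0 / +4.4 | +1.4 / +3.1 |
| 180 days | -4.2 / -8.1 | -4.9 / -9.5 |

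For DOR, expected responders are 17 × 0.23 = 3.9 to 17 × 0.44 = 7.5 in NSCLC, and 25 × 0.15 = 3.75 to 25 × 0.35 = 8.75 in gastric. One responder's death is thus 1/8.75 = 11% to 1/3.75 = 27% of responders.

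**The case against.** Several points on the other side have force.

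- **The drug.** The natural reading of last dose is any study drug, since SAP 4.1 defines both agents as study drugs and the exposure and TEAE definitions say so. That makes this part a wording fix, though a needed one.
- **Openness.** The SAP states its rule, with a reason, in the text and again in Table 3. What is missing is its acknowledgement as a change in Section 5.
- **Operational need.** The Protocol does not say how to date discontinuation when a subject dies while doses are held, so a day window can be defended as a way to apply its rule. That is fair, but 7 days does not match the intervals the documents allow.
- **The gaps.** Protocol Section 8 allows the ±2 days only if doses stay suitably separated. A delay of 21 days or more is a possible reason to stop, not an automatic one, so 27 days is not a firm maximum. Pembrolizumab must still be given if PEGPH20 is held on Day 1 of a later cycle. The exposure rules were not written to define PFS. The 21-day gap on pembrolizumab alone and postponed cycles remain in any case.
- **Size.** The death count is unknown, and documented clinical progression, already an event, will capture some of these subjects. PFS is also reported for the escalation and combined groups, which the simulation does not cover.
- **Scope.** Post-discontinuation deaths and the DOR definition come from the Protocol. They justify supplementary analyses only.

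**Conclusion.** The concern holds. Applied as written, the SAP gives a PFS endpoint that differs from the Protocol's for deaths from day 8 of an on-treatment dosing gap, and for deaths after discontinuation but within 7 days of the last dose. Section 5 does not acknowledge this. In the allowed gaps, 27% to 70% of days are outside the window. The firmest case is pembrolizumab alone at 62%, reading last dose as any study drug.

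The effect is modest: about +2.4 points (NSCLC) or +1.4 points (gastric) in 6-month PFS per on-treatment death in such a gap, within sampling error and resting on the assumed event-time model. The number of such deaths is not given, and the net direction against the Protocol is unknown. PFS and DOR are secondary and untested. This should be corrected, but it does not threaten the primary analysis.

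**What to change.** 1. In SAP 4.7.1 and Table 3, state that last dose means the last dose of any study drug.
2. Replace the fixed 7-day window with the Protocol's rule, stating which recorded date marks discontinuation. Otherwise reconcile the two documents so that deaths in allowed dosing gaps or on pembrolizumab alone count as events.
3. Beside the current analyses, add a PFS analysis that counts every death without prior progression on its date, including subjects with no post-baseline scan. Add a DOR analysis ending at the earlier of progression or death.
4. Tabulate by cancer type the number of deaths censored and the time from last scan to death.
5. List the change in SAP Section 5.

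The cost is one derivation rule, two supplementary tables, one count table and a Section 5 entry. Death dates are already collected for OS. The supplementary estimates may be less favourable. They may instead be higher at early times if deaths come late, possibly after other therapy. For that reason they should sit beside the Protocol-defined analyses and not replace them.

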#### Progression-free Survival per irRC

PFS per irRC will be defined analogous to PFS per RECIST v1.1 by replacing RECIST v1.1 progression by irRC progression (irPD). In the schema shown in Table 3, replace 'radiological' disease progression per RECISIT v1.1' by irPD and 'First date of radiological disease progression' by 'First date of irPD'.

Outcome	Situation	Date of Progression or Censoring
PFS Event	Radiological disease progression per RECIST v1.1 at scheduled or unscheduled visits or at End of Treatment visit	The earliest date of radiological disease progression, documented clinical progression, or death
	Documented clinical progression	
	No radiological or documented clinical disease progression, do not die within 7 days of the last dose, and have adequate tumor assessment at both Baseline and post-Baseline	Date of last adequate tumor assessment
Censoring for PFS (If no PFS	Discontinuation of treatment due to reasons other than radiological disease progression, or documented clinical progression	
Event)	Death after 7 days of the last dose	
	No documented clinical disease progression, do not die within 7 days of the last dose, and had no adequate tumor assessment at either Baseline or post-baseline	First dose date

Table 3:Scheme of Events and Censoring for PFS per RECIST v1.1

#### **Overall Survival**:

Overall Survival (OS) is defined as the time from the first dose date until death from any cause. OS data from surviving subjects will be censored at date of the last contact. OS (in months) will be calculated as:

(Death or censoring date – First dose date + 1) / 30.4375

To determine the date of the last contact, the latest date of the following should be used:

- Hospitalization admission and discharge dates
- Dosing dates
- Laboratory test, vital signs test and 12-Lead Electrocardiogram (ECG) test dates
- Immunogenicity assessment dates
- AE start and stop dates (full dates)
- Cancer therapies/medications/resections/radiation start and stop dates (full dates)
- Tumor assessment dates
- Brain scan dates

- Last known alive dates collected in long-term follow-up period
- Other clinical data which can confirm the subject's survival status

#### 4.7.2 Analysis of Unconfirmed/Confirmed ORR, DCR and DOR

The primary efficacy endpoint of the study in Dose Expansion portion is PEGPEM treatment effect on confirmed ORR based on tumor assessments from the Investigator using RECIST v1.1. The statistical hypothesis tests for the primary endpoint are as follows:

- NSCLC cancer type:  $H_0$ : ORR  $\leq 23\%$ ;  $H_1$ : ORR > 23%
- Gastric adenocarcinoma cancer type:  $H_0$ : ORR  $\leq 15\%$ ;  $H_1$ : ORR > 15%

The hypothesis tests will be conducted using the one-sided exact binomial test at the significance level of 0.1. Thus, confirmed ORR and its two-sided 80% exact confidence interval will be provided to test each of the hypotheses above. If the lower limit of the exact confidence interval lies above 23% or 15% for NSCLC or gastric adenocarcinoma cancer types respectively, the respective null hypothesis will be rejected concluding a statistically significant effect of PEGPEM treatment in the respective cancer type. In addition, best overall response data will be summarized in frequency and percentage format by cancer type and the two-sided, exact 80% confidence intervals for the unconfirmed ORR and DCR will also be provided. Further, median DOR and its 80% confidence interval will be calculated and reported. Unconfirmed/confirmed ORR, DCR, and DOR will also be calculated based on irRC and displayed in summary tables and listings.

Additional efficacy analyses of ORR, DCR, and DOR related to NSCLC cancer type will also be performed using RECIST v1.1 data from Imaging Endpoints.

Note: Halozyme made the decision to discontinue further enrollment into the study on 31 May 2018. At the time of the early termination, a total of 25 gastric adenocarcinoma cancer subjects and 17 NSCLC subjects have been enrolled in the Dose Expansion portion. The planned sample size in the Dose Expansion portion is approximately 51 subjects (approximately 30 with HA-high tumors in NSCLC and approximately 21 with HA-high tumors in the gastric adenocarcinoma cohort). Therefore, a caveat regarding the interpretation of the results will be provided for the NSCLC cohort which is underpowered because of the early termination.

#### 4.7.3 Analysis of PFS and OS

The PFS based on the RECIST v1.1 and irRC, and OS will be analyzed in summary tables by cancer type for the Dose Escalation portion, Dose Expansion portion, and all subjects in both portions.

The PFS based on the RECIST v1.1 and irRC, and OS will be presented by listings for both Dose Escalation and Dose Expansion portions. KM plots will also be constructed for PFS based on the RECIST v1.1 and OS for the Dose Escalation portion, Dose Expansion portion, and all subjects in both portions.

Additional efficacy analyses of PFS related to NSCLC cancer type will also be performed using RECIST v1.1 data from Imaging Endpoints.

#### 4.7.4 Exploratory Analyses

PD-L1 expression levels in tumor tissues, plasma HA and tumor HA will be presented in data listings. No formal analysis regarding exploratory endpoints will be conducted.

#### 4.7.5 Adjustment for Covariates

Not applicable.

#### 4.7.6 Multicenter Studies

The center effect will not be considered for this study.

#### 4.7.7 Multiple Comparisons/Multiplicity

There will be no adjustment for multiple hypothesis testing.

#### 4.8 Subgroup Analysis

No subgroup analyses are planned.

#### 4.9 Safety Evaluations

Safety evaluations include exposure to study medications, DLTs, adverse events (AEs), serious adverse events (SAEs), ECGs, vital signs, clinical laboratory and ECOG performance status. All AEs will be coded using the MedDRA. All safety summaries will be produced by cancer type and overall using the subjects in the Safety Population. The summary of DLTs in the Dose Escalation portion will be performed by cancer type, dose level and in total based on the DLT Evaluable Population.

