11. STATISTICS

11.1. Statistical Methods

In general, continuous variables will be summarized using descriptive statistics (N, mean, standard deviation, median, minimum, and maximum). Categorical variables will be presented using frequencies and percentages. Dose escalation data summaries will be presented by PEGPH20 dose level. All statistical analyses and data listings will be performed using SAS version 9.3 or higher (Cary, NC).

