11.1.7. Analysis of Treatment Exposure

The study medication exposure will be summarized using the Safety Population by dose level. Study medication exposure will include exposure duration, dosing cycles, dosing information for study medication, such as number of doses, relative dose intensity, and dose changes.

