11.1.8. Safety Analyses

All safety parameters will be summarized using the Safety Population by dose level will be descriptive in nature. No inferential statistical tests will be conducted for safety parameters.

All AEs will be presented in incidence tables coded by the Medical Dictionary for Regulatory Activities (MedDRA) Preferred Term and System Organ Class.

Additionally, separate AE incidence tables, coded by MedDRA term, will be presented by: 1) toxicity grade (severity) graded by the CTCAE and 2) relationship to study medication (PEGPH20 and pembrolizumab).

All AEs, SAEs, AEs leading to treatment discontinuation, and deaths occurring during the study will be summarized.

In addition, subjects who experienced TE will be summarized by SMQ term and MedDRA preferred term by grade.

Laboratory parameters and vital signs and the corresponding change from baseline over time will be summarized using descriptive statistics.

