#### 4.4.2 Safety Population

The Safety Population analysis set is defined as all enrolled subjects in either Dose Escalation or Dose Expansion portion of the study, who receive at least 1 dose of any study medication (PEGPH20 or pembrolizumab). The Safety Population will be used for drug exposure, demographics and safety analyses, including AE, labs, and deaths. Subjects will be analyzed according to the initial cohort actually assigned.

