#### 4.9.4 Analysis of AEs

Only TEAEs will be tabulated by system organ class or standard MedDRA query (SMQ) or high level term, and preferred term for the subjects in the Safety Population by cancer type and in total. Summary tabulations include the following:

- An overall summary of TEAEs.
- Grade 3 or higher TEAEs
- Drug-related TEAEs
- Grade 3 or higher drug-related TEAEs
- TEAEs with outcome of death
- Treatment-emergent serious AEs (SAEs)
- PEGPH20 related treatment-emergent SAEs
- Pembrolizumab related treatment-emergent SAEs
- TEAEs leading to discontinuation of study drug
- TEAEs related to PEGPH20 leading to discontinuation of PEGPH20
- TEAEs related to pembrolizumab leading to discontinuation of pembrolizumab
- Summary of Treatment-emergent thromboembolic events by standard MedDRA query (SMQ)
- Summary of Treatment-emergent serious thromboembolic events by SMQ
- Bleeding TEAEs by SMQ
- Musculoskeletal TEAEs by MedDRA high level term.

Subjects experiencing the same AE more than once will have that event counted only once within each body system, and once within each preferred term in all summary tabulations. Listings will be provided for AEs leading to death, SAEs, grade 3 and above AEs, and AEs leading to discontinuation of study drug. Additionally, by-subject listings of the AEs will be presented including, but not limited to, verbatim term, preferred term, system organ class, NCI-CTCAE grade, and relationship to study drug.

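### Apart from DLTs (by dose level) and exposure (by portion), the SAP tabulates safety by cancer type and overall; the protocol requires PEGPH20 dose level, and SAP Section 5 does not declare the change.

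*SAP*

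**What the plan says.** The protocol sets the grouping in three places:

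- Section 11.1, for escalation data generally: "Dose escalation data summaries will be presented by PEGPH20 dose level".
- Section 11.1.7, for exposure: "The study medication exposure will be summarized using the Safety Population by dose level".
- Section 11.1.8, for safety: "All safety parameters will be summarized using the Safety Population by dose level".

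The SAP sets a different one. Section 4.9 gives the general rule: "All safety summaries will be produced by cancer type and overall using the subjects in the Safety Population". Section 4.9.4 repeats it for adverse events, which are tabulated "for the subjects in the Safety Population by cancer type and in total". Sections 4.9.5 (vital signs), 4.9.6 (laboratory) and 4.9.7 (ECG) use the same cancer-type and total columns.

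There are two exceptions. DLTs in Dose Escalation are tabulated by cancer type, dose level and total (4.9 and 4.9.3). Exposure measures, from treatment duration to "relative dose intensity by cancer type and in total separately for the Dose Escalation portion and the Dose Expansion portion", are split by portion but not by dose level.

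The SAP's Safety Population (4.4.2) takes in "all enrolled subjects in either Dose Escalation or Dose Expansion portion of the study". Section 5 of the SAP lists two changes from the protocol: the definition of the Tumor Response Evaluable Population, and the use of local as well as central laboratory data for worst-grade and shift tables. The change of grouping for safety is not there.

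**The concern.** The tables pool subjects who were treated differently. Escalation cohorts may run from 1.0 to 4.0 µg/kg of PEGPH20 or higher, while expansion uses a single dose. The portions also differ in pembrolizumab dose (2 mg/kg against 200 mg) and in the prior therapy required or allowed.

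The protocol itself expects a dose relation: Section 10.8 says that significant musculoskeletal events become more likely as the PEGPH20 dose rises. The SAP's musculoskeletal TEAE table nevertheless combines all doses.

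Two sets of results lose their summary table:

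- **Dose Escalation.** Safety and tolerability is a primary objective. The DLT table covers only the first 21 days. It also counts a Grade 3 musculoskeletal event only if it fails to fall to Grade 2 or below within 48 hours (Protocol 6.1.1). Toxicity by dose that comes later, or that settles sooner, appears in no planned summary.
- **Dose Expansion.** Incidence of adverse events and changes in laboratory values, ECG and vital signs are secondary endpoints of this portion (SAP 4.3.2). No planned table reports them for this portion alone.

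**Working it through.** **Comparison of the rules**

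| Output | Protocol | SAP | Dose level kept? |
|---|---|---|---|
| DLTs | Escalation data by dose (11.1) | Cancer type, dose level, total (4.9, 4.9.3) | Yes |
| Exposure | By dose (11.1.7) | Cancer type and total, by portion (4.9.2) | No |
| Adverse events | By dose (11.1.8) | Cancer type and total (4.9.4) | No |
| Vital signs | By dose (11.1.8) | Visit, cancer type and total (4.9.5) | No |
| Laboratory | By dose (11.1.8) | Cancer type and total (4.9.6) | No |
| ECG | By dose (11.1.8) | Cancer type and total (4.9.7) | No |

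The bulleted list in SAP 4.9.4 holds 15 TEAE tabulations, from the overall summary to musculoskeletal events. None names dose level or portion: 0 of 15.

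**Scale of the pooling**

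There is no figure in the plan to reproduce. The documents do not give the RP2D, the levels actually dosed or the number of escalation subjects, so what follows rests on assumptions.

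Inputs:
- Expansion enrolment at termination: 25 gastric + 17 NSCLC = 42 (SAP 4.7.2). Assumed: all 42 were dosed at the RP2D.
- Subjects per escalation level: 3 to 6 (the 3+3 design). Assumed: no cohort was enlarged.
- Levels dosed: assumed 2 to 5.

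Share of the pooled Safety Population not assigned to the RP2D:

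*s* = (subjects at other levels) / (42 + escalation subjects at the RP2D + subjects at other levels)

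- Smallest: one other level of 3, with 6 at the RP2D. *s* = 3 / (42 + 6 + 3) = 3/51 = 0.059.
- Largest: four other levels of 6, with 3 at the RP2D. *s* = 24 / (42 + 3 + 24) = 24/69 = 0.348.

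If the event rate is *r* at the RP2D and *o* at the other doses, the pooled rate is (1 − *s*)*r* + *s·o*, so

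pooled rate − *r* = *s* × (*o* − *r*).

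For an assumed gap of 20 percentage points:

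- 0.059 × 20 = 1.2 points
- 0.348 × 20 = 7.0 points

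The pooled rate is too low if the other subjects were below the RP2D and had fewer events, and too high if they were above it and had more.

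**The case against.** The strongest reply has five parts.

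1. **The SAP does classify subjects by cohort.** Section 4.4.2 says "Subjects will be analyzed according to the initial cohort actually assigned", and SAP Table 1 ties each escalation cohort to a PEGPH20 dose. That rule assigns subjects to groups but does not set table columns. Sections 4.9 and 4.9.4 to 4.9.7 do that, and they use cancer type and a total. Similarly, planned dose intensity in 4.9.2 is calculated from the cohort's own dose, but the result is not tabulated by dose.

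2. **The protocol is not uniform.** Its synopsis names no grouping for safety, and the sentence in 11.1.8 is badly constructed. But the synopsis is silent rather than contrary, and 11.1 and 11.1.7 are clear.

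3. **The protocol does not require a split by portion for safety.** This stands. Taken literally, a by-dose table would put expansion subjects in the same column as escalation subjects at the RP2D. The departure from the protocol is the loss of dose level. The separate expansion table is a recommendation, based on the expansion secondary endpoints and on the SAP's own practice for efficacy (4.7) and exposure (4.9.2).

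4. **The numbers are soft.** This also stands. The 20-point gap comes from no document. Cohorts may be enlarged, and further levels may be opened. With 6 rather than 3 subjects at the RP2D, the upper share is 24 / (42 + 6 + 24) = 24/72 = 33%. The range also describes only the total column; each cancer-type column has its own denominator. The finding does not depend on these figures.

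5. **Little turns on it.** Safety is descriptive, by-subject listings are planned, and DLTs are shown by dose. That limits the consequence, but listings do not give incidence by dose, and the protocol asked for summaries.

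**Conclusion.** The concern holds. Outside DLTs, the SAP replaces the protocol's dose-level grouping of safety and exposure with cancer type (and portion, for exposure), and Section 5 does not say so. This is a stated rule that conflicts with the protocol, not missing detail: following the SAP as written produces none of the protocol's by-dose summaries of adverse events, laboratory values, vital signs or ECG.

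The size is 0 of 15 TEAE tables by dose or portion. Under the assumptions above, 6% to 35% of the pooled population was assigned to a dose other than the RP2D. That would shift a pooled rate by 1.2 to 7.0 points for each 20-point difference in event rate. The direction is unknown, and the shift is an illustration rather than an estimate.

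The consequence is confined to final reporting. The expansion dose was to be chosen from Cycle 1 safety review (Protocol 6.1.1), which these tables do not affect. The change should be made, but it does not threaten the primary analysis.

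**What to change.** In SAP 4.9, 4.9.2 and 4.9.4 to 4.9.7, specify the safety and exposure tables as follows:

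- Dose Escalation by PEGPH20 dose level, using the initial cohort as 4.4.2 already provides, with a footnote wherever a subject's dose was later escalated.
- Dose Expansion separately, by cancer type.
- A total column.

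If the sponsor judges some by-dose tables not worth producing because the cells are small, list each in Section 5 with the reason. The same check should cover baseline tables: Protocol 11.1.5 asks for demographics by dose level in escalation and separately for expansion, while SAP 4.6 groups by cancer type, again without a Section 5 entry.

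The cost is extra table columns from data already held. Escalation cells will be small, about 3 to 6 subjects per level before any split by cancer type, so counts should be shown beside percentages.
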